We will partner with Mental Health America (MHA), the nation's largest mental health advocacy organization, to design and pilot a highly personalized messaging intervention for depression and anxiety. We will use an iterative design and development process that provides a voice to end-users in message and content creation.²⁵ We will pilot our automated, adaptive DMHI against a randomized version of the intervention and against an active control using a sequential multiple assignment randomized treatment (SMART) design, which targets those disengaged users for additional human support. The *adaptive intervention* will be powered by reinforcement learning to deliver tailored SMS messages based on user profiles and the ways in which a user interacts with the intervention system, along with links to longer psychoeducational content. The *randomized intervention arm* will not personalize the messages, but will still be an active treatment. The *active control* will provide, via a URL, brief psychoeducational content, but will not include the messaging component.

This project has the following three overarching aims:

Aim 1. Develop an adaptive messaging service for young adults that personalizes messages and psychoeducational content to the needs and preferences of an individual.

Aim 2. Evaluate the feasibility of conducting a SMART trial in which 120 young adults screening positive for depression or anxiety on the MHA website will be randomized to receive the adaptive (personalized) messaging intervention, a randomized version of the intervention, or an active control condition. Participants who meet criteria for non-engagement with the messaging interventions during the first 2 weeks will be randomized to receive coaching or continue without coaching for the remaining treatment period. Feasibility criteria include successful recruitment of participants, attaining 80% completion of research assessments, and <30% treatment dropout in at least one treatment condition. We will pilot the following analyses:

Aim 2a. Evaluate the effectiveness of messaging interventions, compared to waitlist control, in reducing psychological distress and secondary outcomes (depression and anxiety symptom severity, suicidal ideation, openness to therapy, and interest in formal treatment), and engaging treatment targets (subjective and objective engagement, behavioral activation, dysfunctional attitudes, coping skill use).

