Statistical Analysis Plan for clinicaltrials.gov

Official Title: Digital Mental Health Service for Non-Treatment Seeking Young Adults

NCT Number: NCT04948268

Grant Number: R34MH124960

Northwestern University Social and Behavioral Institutional Review Board Number: STU00214822

Statistical Analysis Plan

Aim 2. Feasibility

The primary aim of this study will be to evaluate the feasibility of conducting a larger SMART trial. Feasibility will be determined by:

1. meeting recruitment and enrollment goals;
2. obtaining at least 80% of follow up self-report data at primary endpoints; and
3. maintaining dropout below 30% across treatment conditions.

Descriptive statistics will be used to summarize recruitment, retention, completeness of self-report measures, and patterns of missing data. These analyses will inform the suitability of procedures for a future fully powered trial.

Aim 2a. Effectiveness of messaging interventions relative to active control

To evaluate the effects of the adaptive and randomized messaging interventions relative to the control condition, we will model trajectories of the primary outcome (psychological distress; K10) and secondary outcomes (PHQ-9, GAD-7, DSI-SS, and CB-RSS). For each outcome, we will estimate a generalized linear mixed model (GLMM) with one model per outcome, fixed effects for treatment arm, time, and the treatment by time interaction, a participant-level random intercept, an autoregressive correlation structure for repeated observations, and an identity link for normally distributed outcomes, with alternative link functions used as appropriate based on distributional properties. The primary inference will focus on the treatment by time interaction to determine whether either intervention produces a different rate of change over time compared to control. Secondary models will control for baseline demographic covariates (e.g., age, sex, race, ethnicity).

Controlling for missing data and bias. Should more than 5% of the outcome data be missing, we will examine the data for missing mechanisms and use multiple imputation rather than complete case analysis for the primary analysis to avoid bias, combining results from 5 imputed datasets using “mice”.

Aim 2b. Effectiveness of adaptive versus randomized messaging

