If the treatment by time interaction indicates a significant difference between at least one messaging intervention and the control group for a given outcome ($p < .05$), as described in 2a, we will compare the adaptive and randomized messaging interventions for that outcome using the same GLMM approach, restricted to the 2 treatment arms. Outcomes will include the primary clinical outcome measure (K10) and secondary outcome measures (PHQ-9, GAD-7, DSI-SS, CB-RSS). The second primary outcome, engagement duration (time from first message received to last participant interaction), will be summarized descriptively by reporting means and standard deviations, and will be further explored using distribution-appropriate comparisons, as needed.

Aim 2c. Effectiveness of coaching for early disengagement

Participants in the intervention arms who meet predefined criteria for disengagement during the first 2 weeks will be re-randomized to receive coaching or continue without coaching. Analyses will use the same GLMM methods described in Aim 2a incorporating coaching as a covariate to explore whether coaching improves: engagement outcomes (engagement duration, response percentage, number of URL clicks), outcomes (K10, PHQ-9, GAD-7, DSI-SS, CB-RSS). Given the limited statistical power for this embedded re-randomization, results will be summarized descriptively, reporting model coefficients and confidence intervals rather than conducting formal hypothesis tests.

Aim 2d. Exploratory predictors of early disengagement

The need for coaching will be defined as meeting the disengagement criterion during the first 2 weeks. We will compare baseline demographic, clinical, and attitudinal variables between participants who do and do not meet this criterion. Continuous variables will be compared using the Wilcoxon rank sum test, and categorical variables will be compared using Pearson's chi squared test or Fisher's exact test when expected cell counts

are small.

In addition, exploratory predictive models such as random forests will be considered to evaluate whether combinations of baseline variables can classify participants who are likely to disengage early. These analyses are exploratory and intended to generate hypotheses for future trials.

Aim 3. Experimental therapeutics modeling

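### Five imputations are few for a p<.05 gate: in borderline cases the random seed can decide whether Aim 2b is run (minor, nearly free to fix)

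*SAP*

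**What the plan says.** SAP, Aim 2a, paragraph on missing data and bias: the trigger is "Should more than 5% of the outcome data be missing". Multiple imputation then replaces complete-case analysis as the primary analysis, "combining results from 5 imputed datasets" with mice. The SAP states no seed, no rule linking the number of imputations to the amount of missing data, no Monte Carlo error check and no degrees-of-freedom rule.

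SAP, Aim 2 Feasibility: one success criterion is "obtaining at least 80% of follow up self-report data at primary endpoints", so up to 20% missing is acceptable. A separate criterion is "maintaining dropout below 30% across treatment conditions".

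SAP, Aim 2b: the comparison of adaptive with randomized messaging is made only if the Aim 2a interaction "indicates a significant difference between at least one messaging intervention and the control group for a given outcome", at p<.05. SAP, Aim 3: mediation is modelled only where the intervention has a significant effect on the outcome and on the target.

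Protocol section 3.0: 40 participants per group, 80% power for d=0.64, and an expected effect of about d=0.38 for treatment against control.

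**The concern.** Multiple imputation with a finite number m of datasets adds Monte Carlo noise to the pooled estimate, to its standard error and to the degrees of freedom. All three feed the p-value. Relative efficiency, the usual argument that 5 is enough, describes only the point estimate.

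This matters here because the p-value does more than summarise evidence: it determines which later analyses exist. The gate is applied to five outcomes (K10, PHQ-9, GAD-7, DSI-SS, CB-RSS), each with two messaging arms that can open it. If a result lies near the threshold, rerunning the same code on the same data with another seed can open or close the gate. The added noise also costs a little power in a trial that expects an effect smaller than it is powered to detect.

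**Working it through.** **Inputs from the documents.** m=5; imputation trigger 5%; tolerated missing self-report data 20%; gate p<.05 (taken as two-sided, since the SAP does not say); 40 per arm; d=0.64 and d=0.38.

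**Assumed input.** The FMI is not in the documents and is not the same as the missing fraction. The range 0.05, 0.10, 0.20 is shown.

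**The plan's own figure.** With 40 per arm the non-centrality is d × √(40/2) = 0.64 × 4.472 = 2.86. The normal approximation gives Φ(2.86 − 1.96) = 81.7%, and the noncentral t gives 80.7%. The stated 80% reproduces, with no allowance for missing data. At d=0.38 with complete data the power is 38.9%.

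**Point-estimate noise.** Scale the many-imputation variance to 1, so the within-imputation part is 1 − FMI and the between-imputation part B is FMI. The pooled variance is T = W + (1 + 1/m)B. The Monte Carlo SE as a share of the total SE is √(FMI/m), and relative efficiency is 1/(1 + FMI/m). For m=5:

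| FMI | √(FMI/5) | 1/(1 + FMI/5) |
|---|---|---|
| 0.05 | 0.10 | 99.0% |
| 0.10 | 0.14 | 98.0% |
| 0.20 | 0.20 | 96.2% |

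So efficiency looks good, yet at FMI 0.20 the estimate still moves by a fifth of its standard error from seed to seed, and B is itself estimated on only m − 1 = 4 degrees of freedom.

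**Effect on a borderline p-value.** Fix the many-imputation z at 1.96. Draw the pooled estimate with variance FMI/m and B as FMI × χ²(m−1)/(m−1), and apply Rubin's rules with Barnard-Rubin degrees of freedom (complete-data df 120 − 3 = 117). The 5-95% range of p over seeds is:

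| FMI | m=5 | m=50 |
|---|---|---|
| 0.05 | 0.036-0.080 | 0.047-0.059 |
| 0.10 | 0.030-0.099 | 0.044-0.063 |
| 0.20 | 0.022-0.138 | 0.040-0.070 |

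Using complete-data df 78 (two arms of 40) changes little. Put another way, at FMI 0.20 and df 78, a dataset whose many-imputation p is 0.03 passes the gate with 72% of seeds at m=5 and 99.7% at m=50.

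**Effect over whole trials at d=0.38.** The non-centrality after missing data is 0.38 × √20 × √(1 − FMI), that is 1.66, 1.61 and 1.52. Power uses df 78.

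| FMI | two seeds disagree on p<.05, m=5 | power, m=5 | power, m=50 |
|---|---|---|---|
| 0.05 | about 5% | 36.8% | 36.9% |
| 0.10 | about 7% | 34.6% | 35.5% |
| 0.20 | about 11% | 29.9% | 31.9% |

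With m=50 the disagreement is 1-3%. With m=20 at FMI 0.20 it is already down to 4.9%. Where power is near 79% (non-centrality 2.8), m=5 gives 76.2% against 79.0% for m=50 at FMI 0.20.

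**Validity.** Under no effect, rejection stays just below 5% (about 4.7%) for m=5, 20 and 50.

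**Cross-check.** 600 simulated trials of 40 against 40 (five visits, monotone dropout, 20% missing, d=0.64, test of the slope difference) gave an FMI of about 0.24. Two seeds with m=5 disagreed in 13% of trials, and power was 63.2% with m=5 against 68.3% with m=100. FMI 0.20 is therefore a reasonable value at the 20% boundary but not a strict ceiling.

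**The case against.** The strongest reply is that this hardly matters in this trial. The primary aim is feasibility. Protocol section 3.0 uses the size of the effect, not its p-value, as the benchmark for a larger trial. Engagement duration is described without passing the gate, Aim 2c has no formal tests, and Aim 3 is exploratory. The 20% figure is the edge of failure rather than the expectation, and at FMI 0.05 the loss is negligible. The p-value ranges are conditioned on a result at the threshold: at FMI 0.20 and m=5, a result with z=3.0 passes with 99.6% of seeds and one with z=1.0 with essentially none. All of this stands, and it is why the point is minor. It does not remove the point, because the SAP still lets a p<.05 threshold decide which comparisons are made.

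Two stronger readings are tempting and are not supported:

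- **That the plan tolerates 30% missing outcome data.** The 30% criterion concerns dropout. The protocol's Aim 2 reads "attaining 80% completion of research assessments, and <30% treatment dropout in at least one treatment condition", which lists treatment dropout separately from assessment completion. Assessments are REDCap surveys paid for individually (protocol sections 5.0 and 14.0), so someone who stops using the messages can still supply K10 data. Only the 20% is a tolerance for missing data.
- **That the primary analysis is invalid.** Five imputations introduce no bias and do not inflate type I error. Most of the fall from 80% power comes from the missing data themselves.

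Fixing a seed answers only part of the concern: it makes the result repeatable but does not reduce the Monte Carlo error.

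**Conclusion.** The point holds as a minor one. With up to 20% missing data accepted and a hard p<.05 gate, m=5 leaves avoidable seed dependence in borderline results. At the expected d=0.38, about 5% to 11% of trials would change sides of the gate between two seeds, against 1-3% with m=50. The power cost is from under 1 to about 2 points there, and about 3 points at FMI 0.20 where power is near 79%.

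These figures rest on an assumed FMI of 0.05 to 0.20, a two-sided test and Barnard-Rubin degrees of freedom. If missingness ends near the 5% trigger, the effect is small; if the FMI somewhat exceeds 0.20, as in the simulated trials, it is somewhat larger.

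**What to change.** In the SAP's missing-data paragraph under Aim 2a, replace the figure of 5 with a larger number of imputations: at least 20, and 50 for preference. State that Rubin's rules are used with Barnard-Rubin degrees of freedom, and record the seed in the analysis code so that the result can be repeated. Nothing else in the model, the estimand or the gate needs to change.

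The cost is one edited sentence and minutes of computing time for 120 participants.

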Aim 2b. Evaluate the effectiveness of an adaptive vs. randomized messaging intervention to reduce psychological distress, increase engagement duration, improve secondary outcomes and targets.

Aim 2c. Evaluate the ability of coaching to improve engagement targets and psychological outcomes.

Aim 2d. Explore participant characteristics and factors associated with the need for human coaching support above and beyond a messaging intervention with randomized and adaptive messaging.

Aim 3: Experimental therapeutics: Explore if engagement targets (subjective and objective engagement) and psychological targets (behavioral activation, dysfunctional attitudes, coping skill use) mediate significant effects for distress observed in Aims 2a, 2b, or 2c.

BACKGROUND:

Most young adults with mental health diagnoses do not seek out in-person mental health care. While young adults are the age group with the highest prevalence (26.3%) of mental health problems, they are the adult age group with the lowest rates of treatment.²⁶ Without early intervention, their symptoms tend to become worse and more chronic.³⁻⁶ We know that digital mental health interventions are effective at reducing affective symptoms,^{15,16} and young people are interested in these interventions.²⁷

Young adults use digital technologies regularly: 96% own a smartphone, and they are the age group most likely to access the internet exclusively through their smartphone.²⁸ Thus, smartphones are a medium with high penetration through which to deliver a digital mental health intervention. Meta-analyses^{15,16,29} have consistently shown that mobile app and browser-based DMHIs can be effective at reducing symptoms of anxiety and depression across randomized controlled trials.²⁹ While DMHIs are effective when used, they often produce high dropout.^{20,21}

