2. Clinical Trial – With 40 participants randomized to each group, we will have 80% power to detect an effect size of $d=0.64$ for the treatment vs. control compassion. The effect sizes related to messaging interventions for depression have not yet been tested across enough trials to estimate effect sizes. However, meta-analyses comparing coached DMHIs to control conditions have shown effect sizes of $gs=0.67-0.70$ for depression and anxiety, which is not significantly different from psychotherapy.⁴¹ Effect sizes for self-guided DMHIs and smartphone interventions are considerably smaller ($gs=0.27-0.43$).^{42,43} It should be noted that choice of control condition can have a substantial impact on effect sizes. For coached DMHIs, the effect-size for trials using WLCs is $g=0.90$, while effect sizes for studies using active controls is understandably smaller, $g=0.38$.⁴¹ Thus, we would expect to see an effect size of approximately $d=0.38$ for treatment vs. control, as these analyses will pool participants across both engaged participants, who do not require a coach, and coached participants. While we acknowledge this effect size is lower than the effects we are powered to detect, it serves as a useful benchmark in determining whether the intervention shows sufficient value to pursue a larger trial.

As the use of machine learning to personalize messages is novel, there are no studies that provide ideal guidance as to the expected effect size for the adaptive vs. randomized intervention comparisons for DMHIs. However, there is considerable research using “computer-tailored” messaging for health behaviors (e.g. smoking cessation, physical activity, diet, mammography). A meta-analysis showed effect sizes of $g=0.12-0.22$ for tailored vs. randomized messaging.³⁵ These algorithms are simpler than those proposed here, typically consisting of decision trees that tailor only on baseline participant characteristics. Based on this literature, we would expect an effect size of approximately $d=0.20$ in analyses comparing the randomized and adaptive arms. Such an effect size would warrant the inclusion of the proposed machine learning algorithms to personalize messages to meet the needs and preferences of users.

- a. Active Control Group (n=40)
- b. Automated Intervention (n=40)
- c. Randomized Intervention (n=40)

4.0 Recruitment and Screening Methods:

(1) Longitudinal Usability Testing:

The sample will be recruited from two sources:

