The clinical trial will utilize a SMART trial design (see Figure below). Participants will be recruited from MHA's website. The first level of randomization is to one of the three treatment conditions: (1) active control (n=40), adaptive intervention (n=40), or randomized intervention (n=40). This level of randomization will provide us with preliminary data on 1) the effectiveness of messaging as an

intervention and 2) the effectiveness and engagement of randomized vs. adaptive versions. The second level of randomization occurs following disengagement (as defined above under "Coaching" within the first two weeks of intervention use). Participants who meet the disengagement criteria from either the randomized or adaptive intervention will immediately be randomized to receive coaching or continue as self-guided. This data will provide us with preliminary information on the need for and value of coaching (Figure below).

Figure. SMART Trial Design

User feedback: When a participant concludes the intervention (up to 10 participants from each treatment combination [e.g., randomized intervention no coaching; randomized intervention + coaching; adaptive intervention no coaching; adaptive intervention + coaching]), they will be asked to engage in a 30-45-minute user feedback interview, to identify problems and deficiencies with the aim of improving the intervention. Participants who discontinue the intervention will be contacted for an interview at the time their discontinuation is confirmed.

Assessment Strategy:

The primary outcome is psychological distress, measured using the Kessler Psychological Distress Scale (K10).⁴⁹ Administration will occur as part of the research protocol via REDCap online. The primary intervention target is engagement length, measured by time from 1st message sent to the last data point obtained via SMS. Secondary outcomes include: depression, measured by the PHQ-9;³⁹ anxiety, measured by the GAD-7;⁵⁰ suicidal ideation, measured by the DS1-SS;^{51,52} and openness to seeking psychological care, measured by the Attitudes Toward Seeking Professional Psychological Help Scale-Short Form (ATSPPH-SF).⁵³

Data will be gathered from patients as outlined in the table below.

Table of Study Assessments and Assessment points

Construct	Measures	Brief Description	Screening	Study Week						
				0	1	4	8	12	16	

PROTOCOL TITLE: Digital Mental Health Service for Non-Treatment Seeking Young Adults

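### SAP Aim 2b plans no adaptive-versus-randomized estimate for a clinical outcome unless a messaging arm first differs from control at p<.05, a condition the protocol does not set

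*SAP*

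**What the plan says.** SAP, Aim 2b, opens with the condition "If the treatment by time interaction indicates a significant difference between at least one messaging intervention and the control group for a given outcome", and the threshold is set "for a given outcome ($p < .05$), as described in 2a". Where it is met, the SAP fits the Aim 2a type of mixed model to the two messaging arms alone, for that outcome. The outcomes covered are K10 and the secondary measures PHQ-9, GAD-7, DSI-SS and CB-RSS. Nothing is planned for a clinical outcome that does not meet the condition. Engagement duration, which the SAP calls its second primary outcome, is summarised descriptively without the condition.

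The Aim 2a model itself is fitted to every outcome without a condition and has "fixed effects for treatment arm, time, and the treatment by time interaction".

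The protocol states the aim without a condition: "Evaluate the effectiveness of an adaptive vs. randomized messaging intervention to reduce psychological distress, increase engagement duration, improve secondary outcomes and targets". Its Clinical Trial Design text (section 8.1) says the first randomization will give preliminary data on "the effectiveness and engagement of randomized vs. adaptive versions". Section 3.0, Sample Size, says "we would expect an effect size of approximately $d=0.20$ in analyses comparing the randomized and adaptive arms" and adds: "Such an effect size would warrant the inclusion of the proposed machine learning algorithms". On the comparison with control, for which it expects d=0.38, the same section says: "While we acknowledge this effect size is lower than the effects we are powered to detect".

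**The concern.** The protocol treats the difference between adaptive and randomized messaging as a question in its own right, and says what size of difference would justify the algorithms. That is a judgement about an estimate, so the estimate has to be available. The SAP makes the planned estimate for each clinical outcome depend on a different question, whether either arm beats control at p<.05, and the protocol itself expects that test to be underpowered.

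If the condition fails for K10, the team has no planned adaptive-versus-randomized result for the primary clinical outcome, and whether to report one becomes a choice made after seeing the data. If the condition holds, the estimate has been selected on the arm-versus-control result. Feasibility, the SAP's stated primary aim, is not affected. What is at stake is the preliminary evidence on personalization that a larger trial would draw on.

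**Working it through.** **Inputs.** From protocol section 3.0: 40 per arm, 80% power at d=0.64, expected d=0.38 for treatment against control, expected d=0.20 between messaging arms. From SAP Aim 2b: p<.05, at least one messaging arm against control, outcome by outcome. From protocol Aim 2: 80% assessment completion, so about 0.80 × 40 = 32 per arm. Assumed, because the documents do not say: two-sided tests, two unadjusted pairwise contrasts, an end-point comparison on the standardized scale, and how d=0.38 divides between the two arms.

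**1. The plan's own figure.** With n=40 per arm the standard error of a standardized difference is √(2/40) = 0.2236. Power at d=0.64 is Φ(0.64/0.2236 − 1.96) = Φ(0.90) = 0.817, or 0.807 by t-test. The stated 80% is reproduced.

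**2. Power at the expected effects.**
- One arm against control, d=0.38: Φ(0.38/0.2236 − 1.96) = Φ(−0.26) = 0.397 (0.389 by t-test).
- Adaptive against randomized, d=0.20: Φ(0.20/0.2236 − 1.96) = Φ(−1.07) = 0.143.

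**3. Chance that the comparison is skipped.** The two tests against control share the control arm, so this was simulated: three independent arm means with SD 1, and the condition met if |z|>1.96 for either arm.

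| d vs control, randomized / adaptive | Skipped, 40 per arm | Skipped, 32 per arm |
|---|---|---|
| 0.38 / 0.38 | 44% | 52% |
| 0.28 / 0.48 | 38% | 47% |
| 0.18 / 0.38 | 57% | 63% |

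**4. Sensitivity.** A more favourable split of 0.38/0.58 gives 22% skipped at 40 per arm. If the condition is read as one 2-df test of all arms, the three splits in the table give 60%, 53% and 69%. The SAP tests slopes, and the documents give no within-person correlation. Change-score models (correlation 0.3 to 0.7) and slope models (random intercept plus AR(1)), with the 0.38/0.58 split included, take the full range to about 6% to 70%.

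**5. Selection when the condition is met.** With a true difference of 0.20 and 40 per arm, the mean estimate among trials that pass is 0.244 (split 0.28/0.48) or 0.271 (split 0.18/0.38). The bias is 0.044/0.2236 = 0.20 and 0.071/0.2236 = 0.32 of a standard error, which is modest.

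**6. What the condition buys.** If all three arms are equal, passing the condition and then rejecting between messaging arms happens in 1.8% of trials per outcome, against 5.0% without the condition. If both messaging arms are at 0.38, the figures are 4.3% and 5.0%. Over five outcomes with all arms equal, at least one 95% CI excludes zero in up to 1 − 0.95⁵ = 22.6% of trials if the outcomes are independent, and less if they are correlated.

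**The case against.** Testing two versions against each other only after one has beaten control is a recognised way to limit false positives, and step 6 shows that it does so. A SAP may add a testing order to an aim that the protocol states in general terms. The unconditional Aim 2a model already contains both arms' effects against control, so the point contrast can be recovered from it. Engagement duration, the result closest to what the adaptive engine is meant to improve, is reported regardless. The information lost is also limited: at 40 per arm the 95% CI half-width is 1.96 × 0.2236 = 0.44, so an estimate of 0.20 would run from −0.24 to 0.64. With a true difference of 0.20, the unmet condition hides a nominally significant difference in at most about 4% of trials (0.145 − 0.107 = 0.038).

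Much of this stands, and it supports keeping the condition for significance claims. It does not support having no planned estimate. The SAP makes no commitment to report the contrast from the Aim 2a model, and an interval for it also needs the covariance of the two coefficients. Low power argues for an interval, and SAP Aim 2c does just that: it reports coefficients and intervals without formal tests because power is limited.

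A reader might infer that the SAP forbids the comparison when the condition fails. It does not. Aim 2b says if, whereas Aim 3 says explicitly that mediation models will not be estimated when their conditions are unmet. A reader might also infer that the SAP contradicts the protocol. The protocol passages state an aim and a purpose, not an analysis rule, so the SAP is narrower than the protocol but does not contradict it.

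**Conclusion.** The point holds for the five clinical outcomes. The SAP sets a rule under which a stated protocol aim can go without a planned answer for K10, and it has no fallback. At the protocol's own effect sizes the planned comparison is skipped for a given outcome in about 38% to 57% of trials. That range assumes an end-point comparison, 40 per arm, two-sided .05, pairwise tests and the three splits shown. It is an illustration, because the documents fix neither the split, the correlation nor the form of the test.

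It would be tempting to add that the estimates which are reported will be seriously distorted. The figures do not support this, since the bias is 0.20 to 0.32 of a standard error at these splits under the pairwise condition. The main harm is non-reporting. Feasibility conclusions and engagement duration are untouched, so this should be corrected but does not threaten the trial.

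**What to change.** Add to SAP Aim 2b: *For K10 and each secondary outcome, the adaptive-minus-randomized difference in rate of change (the arm-by-time contrast, on the model's link scale) will be reported with its 95% CI whatever the Aim 2a result, and labelled descriptive. A p-value or significance claim will be made only where the Aim 2a condition is met.*

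Take both the CI and the p-value from the two-arm mixed model already specified, and run it for every outcome. Taking the interval from the three-arm model and the p-value from the two-arm model could give results that disagree, because their variance and correlation estimates differ.

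The cost is SAP wording and, where the condition fails, running a model that is already specified. No new data are needed. The downside is that readers may treat an interval excluding zero as a test. If all arms are equal, that happens in 5% of trials per outcome, against about 2% under the condition, and for at least one of five independent outcomes in up to about 23%. This is why the descriptive label is needed.
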